- Vaccinated with RSV vaccine during the study period of interest': vaccinated with exposure of interest: e.g. single dose/primary vaccination/at least one dose of the RSV vaccine during the epidemiological year(s) of interest, within the appropriate timeframe for the product to be **effective** prior to modified SARI symptom onset.
- Unvaccinated with RSV vaccine during the study period of interest': did not receive any RSV vaccine during the epidemiological year(s) of interest.
- 'Recently vaccinated with RSV vaccine during the current RSV season': Vaccinated with *exposure of interest: e.g. single dose/primary vaccination/at least one dose* of the RSV vaccine during the epidemiological year(s) of interest, within the appropriate timeframe for the product to be **ineffective** prior to modified SARI symptom onset.
- 'Other':

additional vaccine exposure definitions might be defined depending on the real-life use of the RSV vaccines.

Data sources, data collection

The study uses a combination of primary (e.g., specific laboratory results, vaccine cards) and secondary data sources (e.g., existing hospital databases, vaccine registries and linked data).

After study enrolment, data will be collected directly from the patient or by consulting medical records. Information to be collected at minimum includes date of modified SARI symptom onset, date of hospitalisation, respiratory specimen testing results, and information on the potential confounders and effect modifiers.

Exposure status, RSV vaccine information and date(s) of vaccination(s) will be ascertained by consulting vaccination registries, vaccination cards or medical records (depending on the country and region). Where needed, treating physician or other health care professionals will be contacted to obtain additional information.

Context information on national/regional vaccination recommendations and RSV vaccine label information will be collected from external sources.

Covariates

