11.2 Study Contributors

In this study, the term 'Study Contributor' is used in lieu of 'study site'.

The participating Study Contributors are either individual hospitals or hospital networks. The data collection will be a prospective data collection from primary data sources (e.g., specific laboratory results) and secondary data sources (e.g., existing hospital databases, vaccine registries and linked data). Retrospective data collection will be considered to allow capture of whole epidemiological year data in Study Contributors with late set-up.

¹⁰ The list of countries will be extended as the id.DRIVE network grows.

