11.4 Study period

The study provides continuous (i.e., year-round) RSV surveillance, with a study period lasting minimum one epidemiological year with a possible extension.

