11.8 Exposure

11.8.1 Exposure definitions

11.8.1.1 'Vaccinated with [RSV vaccine name] during the study period of interest'

'Vaccinated' study participants were vaccinated with exposure of interest: e.g. single dose/primary vaccination/at least one dose of RSV vaccine of interest during the epidemiological year(s) of interest, within the appropriate timeframe for the product to be **effective** prior to modified SARI symptom onset.

11.8.1.2 'Unvaccinated with [RSV vaccine name] during the study period of interest'

'Unvaccinated' study participants did not receive any exposure of interest: e.g. single dose/primary vaccination/at least one dose of RSV vaccine of interest during the epidemiological year(s) of interest.

11.8.1.3 'Recently vaccinated with [RSV vaccine name] during the current RSV season'

'Recently vaccinated' study participants were vaccinated with exposure of interest: e.g. single dose/primary vaccination/at least one dose of RSV vaccine of interest during the epidemiological year(s) of interest, within the appropriate timeframe for the product to be **ineffective** prior to modified SARI symptom onset.

11.8.1.4 'Other'

Additional vaccine exposure definitions might be defined depending on the real-life use of the RSV vaccines.

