11.8.2 Exposure ascertainment

Information on all prior RSV vaccine doses will be collected. Vaccination status, vaccination date, vaccine dose and vaccine name and brand information are required. Depending on the Study Contributor, the source for exposure ascertainment will be different and may include vaccination registries, medical records, or vaccination cards. Information on the source documentation of the exposure ascertainment will be collected.

Patients that cannot be classified into one of the exposure categories (i.e., their vaccination status is unknown) will be excluded.

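### The unvaccinated reference group is bounded by the epidemiological year(s) of interest, with no look-back and no anchor to symptom onset, so patients vaccinated earlier can enter it and lower the estimated VE

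*Protocol*

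**What the plan says.** The Abstract (Exposure) and section 11.8.1 name three exposure groups.

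- *Vaccinated* and *recently vaccinated* each carry two conditions. There must be a dose in the window, which 11.8.1 words as "at least one dose of RSV vaccine of interest during the epidemiological year(s) of interest", and the dose must fall in a stated timeframe "prior to modified SARI symptom onset".
- *Unvaccinated* carries only the window. In the Abstract, such a person "did not receive any RSV vaccine during the epidemiological year(s) of interest". In 11.8.1.2, "Unvaccinated' study participants did not receive any exposure of interest" in the same window. The Abstract counts every RSV vaccine here; 11.8.1.2 counts only the vaccine under study.

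A fourth entry, 11.8.1.4 (Other), is optional: "Additional vaccine exposure definitions might be defined depending on the real-life use of the RSV vaccines".

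Section 11.8.2 states that "Information on all prior RSV vaccine doses will be collected", and requires vaccination date and brand. It excludes patients who fit no category and explains this as unknown vaccination status. Section 11.4 describes continuous surveillance "with a study period lasting minimum one epidemiological year with a possible extension". On late sites, section 11.2 says: "Retrospective data collection will be considered to allow capture of whole epidemiological year data in Study Contributors with late set-up".

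**The concern.** The unvaccinated are the reference for every VE estimate, primary and stratified. Two of the three groups are defined by status at symptom onset, and the reference group is defined by calendar window alone. That leaves two gaps.

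First, a dose given before the window does not count. Section 9 reports two RSV vaccines authorised in the EU as of 20 November 2023, and the protocol is dated 07 June 2024, so people vaccinated before a study year can exist from the first season. Extension of the study can add to them. If they keep some protection, the comparator is partly protected and VE is understated. On a one-year window, the vaccinees who say most about duration of protection are also counted as unexposed in objective 2.3.

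Second, a dose given after onset but inside the window removes a patient from the unvaccinated group without placing that patient in either vaccinated group. Exposure status then depends on something that happened after the outcome.

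**Working it through.** The protocol gives no coverage, VE or sample size figure that depends on this definition, so there is no stated number to reproduce. The check is an allocation of dose patterns to the written groups, followed by sizing under assumed inputs.

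**Allocation, reading the definitions literally with a one-year window**

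| RSV dose history | Group under 11.8.1 |
|---|---|
| Never vaccinated | Unvaccinated (reference) |
| Only dose before the window | Unvaccinated (reference) |
| Dose in the window, before onset | Vaccinated or recently vaccinated |
| Only dose in the window, after onset | None of the three named groups |

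The second and fourth rows are the problem.

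**Sizing, doses before the window.** Section 11.12.4 defines VE as (1 − OR) × 100%. Let f be the share of reference-group controls who were vaccinated before the window, and VEr their residual VE. Then

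OR_obs = (1 − VE) / (1 − f × VEr).

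With an assumed true VE of 70%:

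- f = 5%, VEr = 50%: 0.30 / 0.975 = 0.308, VE 69.2%
- f = 10%, VEr = 30%: 0.30 / 0.97 = 0.309, VE 69.1%
- f = 10%, VEr = 50%: 0.30 / 0.95 = 0.316, VE 68.4%
- 10% of controls vaccinated in the current year and 20% earlier, so f = 20/90, VEr = 50%: 0.30 / 0.889 = 0.3375, VE 66.25%
- 10% current and 30% earlier, f = 30/90, VEr = 60%: 0.30 / 0.80 = 0.375, VE 62.5%
- 5% current and 35% earlier, f = 35/95, VEr = 60%: 0.30 / 0.779 = 0.385, VE 61.5%

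The bias is downward whenever f and VEr both exceed zero; only its size depends on the inputs.

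**Sizing, doses after onset.** Suppose these patients are dropped. Let g be the proportion of those unvaccinated at onset who are vaccinated later in the same window. Then

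OR_obs = OR × (1 − g_control) / (1 − g_case).

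With a true VE of 70%:

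- g = 10% in both: 0.30 × 0.90 / 0.90 = 0.300, VE 70.0%
- g_case = 5%, g_control = 15%: 0.30 × 0.85 / 0.95 = 0.268, VE 73.2%
- g_case = 15%, g_control = 5%: 0.30 × 0.95 / 0.85 = 0.335, VE 66.5%

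So there is no bias at equal later uptake, and bias in either direction otherwise.

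**After the fix.** With status fixed at onset and a full look-back, f = 0 and g = 0 in both groups, and the estimate returns to the assumed 70%.

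**The case against.** This is a master template. Section 11.8.1 still holds placeholders, and its window is written in the plural. A Study Requestor-specific protocol could set it to cover every year since vaccines became available, and the first consequence would then disappear. The Other category can take further exposure groups. Annex 1 describes three generic groups, one of them outside the comparison, with proportions drawn partly from vaccination history. The Abstract also provides an expert consensus group to classify exposure. In a first season few people may have been vaccinated before the window, and the effect is then about one percentage point. The bias is downward, so it cannot create effectiveness.

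All of this is fair, and it limits the size of the problem. None of it requires the right allocation. Earlier vaccinees already satisfy the unvaccinated definition, so they need never reach Other. The headings of the vaccinated and unvaccinated groups refer to the study period of interest, which works against reading the window as all years since availability. The Background section says the Master Protocol exists to harmonise exposures, so the wording will carry into the derived protocols. Neither the limitations in section 13 nor the sensitivity analyses in 11.12.4.2 address it.

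The objection has more force on doses after onset. A reader might infer that these patients are routinely excluded under 11.8.2 and that VE is therefore inflated. The documents do not support that. The exclusion is explained as unknown status, whereas these patients have a known, dated status, so they are unassigned rather than clearly excluded. Section 11.8.2 collects prior doses, so later ones would surface mainly through retrospective or registry data, and nothing shows this to be common. The direction of any bias is not fixed.

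**Conclusion.** The definition needs correcting, mainly for the missing look-back. Unless the window is set to cover all years since vaccine availability, patients vaccinated earlier enter the reference group and VE is understated if their protection persists. For an assumed true VE of 70%, the estimate is about 69% with small earlier-year shares (5–10% of the reference, residual VE 30–50%) and about 62% when they are a third of the reference with residual VE 60%. True VE, coverage and residual protection are all assumptions.

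The missing onset anchor is secondary. It leaves one kind of patient without a group. If such patients are dropped, precision is lost, and VE is biased only if later uptake differs between cases and controls.

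It would go too far to call objective 2.3 unanswerable beyond one year. Prior doses and dates are collected, and the window or the Other category could accommodate longer intervals. The defect is that, under a one-year window, the written definition puts those patients in the comparator.

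**What to change.** In the Abstract and section 11.8.1:

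1. Define *unvaccinated* as no RSV vaccine of any brand recorded at any time before modified SARI symptom onset.
2. State that doses after onset are ignored when exposure is classified.
3. Add a category for patients vaccinated only before the epidemiological year(s) of interest. Keep it out of the reference group and use it as the longest time-since-vaccination stratum in objective 2.3.
4. Reconcile the Abstract, which counts any RSV vaccine, with 11.8.1.2, which counts only the vaccine of interest. As written, a recipient of another brand in the window is outside the reference group in one place and inside it in the other.

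This needs protocol wording and derivation code but no new data: section 11.8.2 and Table 1 already capture RSV vaccination history with date and brand. The price is a smaller reference group in later seasons. Under the three coverage scenarios above it falls from 90% to 70% of controls (20/90 = 22%), from 90% to 60% (30/90 = 33%), or from 95% to 60% (35/95 = 37%). The loss should be small in a first season, when few patients have earlier doses, but the later-season figures belong in the Requestor-specific sample size calculations.

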Variables that are potential confounders and/or effect modifiers will be collected at Study Contributors. These include: age, gender, history of selected morbidities of interest (e.g., asthma, lung disease, cardiovascular disease, and immunocompromising conditions)⁷, vaccination against other respiratory pathogens (severe acute respiratory syndrome coronavirus 2 [SARS-CoV-2], influenza, *Streptococcus pneumoniae*), history of prior RSV infection, prior modified SARI hospitalisation(s), pregnancy (and term), smoking history, history of anti-RSV antibodies received either as prophylaxis

⁷ Definitions of the comorbidities of interest will be specified in detail as part of the electronic case report form (eCRF).

or treatment for the current or previous modified SARI episodes, body mass index (BMI), and long-term care facility residence.

RSV testing

Reverse transcription polymerase chain reaction (RT-PCR) or another ribonucleic acid (RNA) amplification system with at least the same sensitivity as RT-PCR (e.g., transcription-mediated amplification [TMA]) will be required to confirm an RSV infection. RT-PCR assays must be used for the detection of at least RSV, SARS-CoV-2, and influenza. Information on the RSV subtypes will be collected to the extent possible, preferably on all confirmed RSV cases when sample quality allows.

Respiratory sampling should preferably be done in both the nasopharynx and oropharynx, using a stiff oropharynx swab or a flexible nasopharynx swab. Additional respiratory specimens are accepted (e.g., saliva/saline mouth wash, sputum, bronchoalveolar lavage, or aspirates), when collected as part of patient diagnostic work-up.

It is recommended that specimens are collected *within 10 days prior to and up to 72 hours after hospital admission* for analysis of the primary objective. All test-negative tests will be re-tested at hospital admission.

Sample size

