Ethical considerations

Study Contributor-specific protocols (developed by the Study Contributors themselves, based on this Study Requestor-specific protocol) will be submitted to relevant independent ethics committee(s) (IECs) following local regulations. Informed consent will be obtained from participants/guardians as specified by the national/regional IEC.

Confidential

Version 2.0

Study limitations

Study limitations include:

- Time-varying confounders and effect modifiers: these include seasonality, RSV subtypes, levels of vaccine-induced and natural immunity in the population, and timing of RSV vaccination programmes. Their complex interplay makes it challenging to disentangle waning of vaccine-induced immunity, differences in VE against different RSV subtypes, and infectionacquired immunity.
- Misclassification of disease status: RSV RT-PCR assays have a high specificity and sensitivity, but a single respiratory swab may miss 50% of RSV infections among older adults. RT-PCR sensitivity is influenced by several factors, including operator sampling technique, type of specimen, number of specimens, and timing of sampling. To explore any potential bias due to disease misclassification, sensitivity analyses regarding time between symptom onset and swabbing are performed.
- Prior infection: Infection-acquired immunity is an effect modifier of VE. Although information on past RSV infection is collected in this study, prior infection may be undocumented (e.g., asymptomatic disease).
- Unaccounted for confounders: these include ethnicity, socio-economic status and frailty. In general, results from this study will be highly specific to its population, and this will need to be carefully considered when generalising or comparing results.

Dissemination

The generic Master Protocol on which this Study Requestor-specific protocol is based (MASTER PROTOCOL Brand-specific respiratory syncytial virus vaccine effectiveness in Europe version 2.0), and its significant amendments, will be listed in the Heads of Medicines Agencies/European Medicines Agency (HMA/EMA) catalogue of real-world data studies. Study reports, each for a specific vaccine brand, will likewise be listed in the HMA/EMA catalogue and will be submitted to peer-reviewed open-source international journal(s).

Updates on study progress will be posted on the id.DRIVE website (https://iddrive.eu).

Funding

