11.6 Definitions

11.6.1 'Hospitalised patient'

A 'hospitalised patient' is defined as a person admitted to the hospital with overnight stay¹⁴. In case of referral to another hospital, the date of hospital admission is defined as the date of first admission.

¹⁴ The patient is hospitalised for minimum one whole night ("one overnight stay").

11.6.2 'Modified SARI patient'

A 'modified SARI patient' is defined as a person hospitalised with a suspicion of a respiratory infection with at least one of the following symptoms:

- cough
- shortness of breath
- fever (≥38 C^o)

with symptom onset within the last 10 days prior to the current hospital admission. This SARI definition is modified from the latest ECDC case definition [15]. Sensitivity analysis will be done applying the WHO-RSV case definition¹⁵ and id. DRIVE case definition¹⁶.

Additionally, the International Classification of Diseases (ICD)-10 codes and corresponding definitions listed below could be used as a guideline to identify potential modified SARI patients (i.e., for screening), if deemed appropriate at specific Study Contributors:

- J00-J06: Acute upper respiratory infections
- J21.0, J21.8, J21.9: Bronchiolitis
- J12-J18: Pneumonia
- J20-J22: Other acute lower respiratory infections
- J40-J47: Chronic lower respiratory diseases

11.6.3 'Study participant'

A 'study participant' is defined as a patient who meets the 'hospitalised patient' AND 'modified SARI patient' definitions, AND fulfils all the inclusion criteria but none of the exclusion criteria.

11.6.4 'Case' ('test-positive case')

'Cases' are study participants who meet the 'modified SARI patient' definition AND have tested positive for at least one RSV RT-PCR or similar molecular assays, with specimens collected within 10 days prior and up to 72 hours after hospital admission. Test-positive cases include laboratory-confirmed coinfections.

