¹⁶ An id.DRIVE definition of SARI (defined as requiring hospitalisation with a suspicion of a respiratory infection with symptom onset within the last 14 days prior to hospital admission, having at least one of the following symptoms: cough, shortness of breath, fever (\geq 38 C°) or sudden onset of anosmia, ageusia or dysgeusia) will be used in sensitivity analyses. This SARI definition is modified from the latest ECDC case definition (specifying "suspicion of respiratory infection"). [EUROPEAN CENTRE FOR DISEASE PREVENTION AND CONTROL (2023). Core protocol for ECDC studies of COVID-19 vaccine effectiveness against hospitalisation with Severe Acute Respiratory Infection, laboratory-confirmed with SARS-CoV-2 or with seasonal influenza - Version 2.0. Available from: https://www.ecdc.europa.eu/en/publications-data/core-protocol-ecdcstudies-covid-19-vaccine-effectiveness-against-0 [Accessed: 17-08-2023]].

¹⁵ A World Health Organisation (WHO)-expanded definition of RSV-SARI (severe disease – defined as requiring hospitalisation AND acute – defined as onset within the last 10 days AND respiratory infection – defined as having at least one of the following: shortness of breath or cough) will be used in sensitivity analyses. [Source: https://www.who.int/teams/global-influenza-programme/global-respiratory-syncytial-virus-surveillance/case-definitions]

11.6.5 'Control' ('test-negative control')

'Controls' are study participants who meet the 'modified SARI patient' definition AND have all respiratory samples being negative for RSV RT-PCR or similar molecular assays, with specimen(s) collected between 10 days prior to and up to 72 hours after hospital admission. Test-negative controls include study participants negative for other pathogens and study participants positive to other pathogens based on specimen(s) collected between 10 days prior to and up to 72 hours after hospital admission.

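### The specimen window for cases and controls is tied to admission and not to symptom onset, so a swab taken before the episode began can set RSV status; the re-test of negatives stands only in the abstract

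*Protocol*

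**What the plan says.** Protocol 11.6.2 defines a modified SARI patient by symptoms "with symptom onset within the last 10 days prior to the current hospital admission".

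Under 11.6.4 a single positive molecular result is enough to make a participant a case, and the only limit on timing is "with specimens collected within 10 days prior and up to 72 hours after hospital admission". Section 11.6.5 makes a participant a control whose samples are all negative, the specimens being "collected between 10 days prior to and up to 72 hours after hospital admission". The abstract's own case and control definitions use the same window. All of these count from admission, and none mentions symptom onset as a limit on the specimen.

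The RSV testing part of the abstract (section 8) adds: "All test-negative tests will be re-tested at hospital admission". That sentence does not appear in 11.5.1, 11.6.4, 11.6.5 or 11.7. Section 11.5.1 says only that extra study sampling may be needed, depending on local practice. Sections 11.2 and 11.7 allow retrospective data collection and retrospective identification of patients from databases or laboratory samples.

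Analyses of the time from onset to swab are foreseen in the abstract's limitations, in 11.12.4.2 and in section 13. The abstract says they are performed; 11.12.4.2 lists them among analyses that can be conducted.

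**The concern.** In a test-negative design the RSV result has to describe the illness that led to admission. Two windows that share the 10 days before admission, with no ordering between them, do not ensure this. There are two possible errors:

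- A negative swab taken before onset, with nothing later, makes a patient with RSV illness a control.
- A positive swab taken before onset makes a patient whose later illness has another cause a case.

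If neither error depends on vaccination, both pull VE towards zero.

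Other parts of the protocol are timed on onset, which makes the gap stand out. Section 11.8.1 times vaccination against symptom onset. Table 1 records RSV earlier in the season, before onset of the current episode, as a history covariate. Under 11.6.4 the same pre-onset positive can also be the outcome.

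The re-test sentence raises a second problem. The abstract requires a step that the body does not, and its wording could mean a new swab or a repeat assay on the old specimen. This master text is the source for Requestor-specific and Contributor-specific protocols, so the ambiguity can be passed down.

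**Working it through.** The plan states no figure on this point, so there is nothing to reproduce. Two checks were made.

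**1. Which date combinations do the definitions allow?** Count in whole days with admission as day 0.

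- Onset: day -10 to day 0, 11 values (11.6.2).
- Swab: day -10 to day +3, 14 values (11.6.4, 11.6.5).
- Allowed pairs: 11 × 14 = 154.
- For onset on day d, the swab days before onset number d + 10. Summing over d = -10 to 0 gives 0 + 1 + ... + 10 = 55.
- Share: 55/154 = 35.7%. Among swabs taken before admission: 55/(11 × 10) = 50%.
- Largest gap: 10 days (swab on day -10, onset on day 0).

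These are counts of permitted combinations. How often they occur is not in the protocol. Requiring the swab on or after onset reduces the 55 to 0.

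**2. What could it do to VE?** All inputs here are assumptions: true VE 70% (OR 0.3), vaccination coverage in true controls p0 = 20%, RSV in 10% of participants, a share q with only a pre-onset swab, and a chance f that such a swab is positive by coincidence. Tests are otherwise perfect and nothing depends on vaccination.

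Vaccination odds in true cases are 0.3 × 0.20/0.80 = 0.075, so their coverage is p1 = 0.075/1.075 = 0.0698.

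Without a re-test:

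- apparent cases: 0.1 × (1 - q + qf) at coverage p1, plus 0.9 × qf at coverage p0;
- apparent controls: 0.9 × (1 - qf) at coverage p0, plus 0.1 × q(1 - f) at coverage p1.

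At the extreme, q = 20% and f = 5%:

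- Cases: 0.081 × 0.0698 + 0.009 × 0.20 = 0.00745 vaccinated out of 0.090; odds 0.0903.
- Controls: 0.891 × 0.20 + 0.019 × 0.0698 = 0.1795 vaccinated out of 0.910; odds 0.2458.
- OR = 0.0903/0.2458 = 0.367; apparent VE = 63.3%.

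With a perfect re-test of negatives, all true cases are found but the 0.009 false cases stay. Cases are then 0.00878 vaccinated out of 0.109, odds 0.0876. Control odds are 0.25, OR = 0.350 and VE = 65.0%.

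Apparent VE (%), no re-test / perfect re-test:

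| q | f = 0 | f = 2% | f = 5% |
|---|---|---|---|
| 5% | 69.9 / 70.0 | 69.3 / 69.5 | 68.5 / 68.7 |
| 10% | 69.7 / 70.0 | 68.5 / 68.9 | 66.8 / 67.4 |
| 20% | 69.5 / 70.0 | 66.8 / 67.9 | 63.3 / 65.0 |

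The f = 0 column isolates missed cases: at most 70.0 - 69.5 = 0.5 points. At the extreme the loss is 70.0 - 63.3 = 6.7 points, of which a perfect re-test recovers 65.0 - 63.3 = 1.7. The loss depends on how common RSV is: the same extreme gives 57.9% with RSV in 5% of participants and 65.9% with RSV in 20%.

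Excluding patients with only a pre-onset swab removes the same share q from every cell in this model, so VE returns to 70%.

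**The case against.** The strongest defence is that the effect may be small. The protocol does not say how many participants would have only a pre-onset swab. Some pre-onset positives will be early detection of the same RSV infection, which makes the coincidental-positive scenario a worst case. The onset-to-swab analyses, the admission-to-swab analysis and the removal of controls with a positive rapid antigen test before admission (11.12.4.2) all bear on the question. This stands as a limit on size. It does not remove the point, because none of these analyses changes the primary definitions.

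A reader might also infer more than the document supports:

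- **That VE would be overstated.** Section 13 does warn of more false negatives among the vaccinated, but attributes this to sensitivity declining over time. That is late sampling, which an on-or-after-onset rule does not address.
- **That the 50% miss rate measures this defect.** The abstract says "a single respiratory swab may miss 50% of RSV infections among older adults". That applies to any single swab, including one taken at admission after onset, so it does not size the pre-onset problem.
- **That the abstract sets a competing window by only recommending it.** Its own case and control definitions use the same window as 11.6.4 and 11.6.5; the recommendation is sampling advice.
- **That sites will classify the same patient differently.** They can, but they work from Contributor-specific protocols, which may settle the matter.
- **That the re-test should simply become mandatory for controls.** Retrospectively identified patients (11.2, 11.7) cannot be re-swabbed, so this would remove those whose only specimen is a pre-admission negative.

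Finally, Figure 1, the schedule of activities, was not available for this check. That the re-test is only in the abstract is established for the text alone.

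**Conclusion.** The point holds in two parts. First, the primary case and control definitions admit specimens taken before the current illness began, and a re-test of negatives cannot undo a pre-onset positive. Second, the re-test is promised in the abstract, absent from the methods text, and unclear about whether a new specimen is meant.

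On the assumed inputs the loss runs from 0.1 to 6.7 points on a true VE of 70%, towards lower VE, and most of it comes from coincidental pre-onset positives. The result rests on misclassification being independent of vaccination and on shares that the protocol does not give, so it shows scale only. The first part is worth correcting because the ordering rule is cheap; the second because the abstract and body need to agree.

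**What to change.** 1. In 11.6.4, 11.6.5 and the abstract's case and control definitions, require the status-defining specimen to be collected on or after symptom onset of the current episode, within the existing admission window. Exclude patients with only pre-onset specimens from the primary analysis and count them in the attrition diagram (11.12.2).
2. Reconcile the re-test statement between the abstract and 11.5.1/11.6.5: either carry it into the body or remove it. If it stays, say whether a new specimen is meant and how retrospectively identified patients are handled.

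Cost: the first change is wording, since onset and specimen dates are already collected. Patients with only a pre-onset specimen leave the primary analysis; their number is unknown. The second change is also wording, unless new swabs are meant, in which case sites that do not already take them would have extra sampling.
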